## 8.4 Missing Data

(ICH E3; 9.7.1, 11.4.2.2. ICH E9;5.3. EMA Guideline on Missing Data in Confirmatory Clinical Trials)

Missing data will be given careful attention in the analysis. In this RCT we have two treatment arms and three fixed times for assessment. It is anticipated that drop-outs from the study will be at random because study participants were considered treatment-seeking. However, it is possible that participants may not attend all follow-ups. Drastically fewer participants in the final analysis would affect study sensitivity and excessive missed follow-ups would potentially bias model parameter estimates. Under the assumption of limited data that is missing completely at random (MCAR) or missing at random (MAR), the mixed-effect model using restricted maximum likelihood estimation is a full information approach and leads to unbiased model parameter estimates. Selection between models with two common covariance structures, Toeplitz and independent errors will be accomplished using the Akaike Information Criterion (AIC).

In the event that assumptions are not met regarding missing value frequency, MAR, or MCAR and missing values are occurring with higher frequency or are truly missing not at random (MNAR), the analysis may be biased. To test the missingness assumptions, missing data will first be summarized by group, time, each design cell, and each of the three covariates, age, sex and body mass index in an effort to graphically or tabularly detect patterns in the variation of missingness. More formally, missing/non-missing will be taken as a dichotomous outcome in a logistic regression for continuous covariates and will be compared with between and within factors and sex using chi-square tests. Significant logistic regression coefficients or significant chi-square tests indicate a pattern of missingness variation that will be identified and reported and whose impact on the analysis will be explained if possible. Model residuals will be evaluated for normality using the Shapiro-Wilk test, homogeneity of variance using Levine's test, and transformations, if necessary, will be chosen from among the Box-Cox transformations.

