### 9.4 Efficacy Analyses

The primary and secondary outcomes will be summarized stratified by treatment group at each study timepoint (baseline, 12-week, 24-week). Our primary analysis will use an intention-to-treat (ITT) analysis that includes all participants who wore the monitor for ≥4 days for 10 hours/day at baseline. The statistical model underlying the analysis a mixedeffects model to examine the main and interaction effects of group (Intervention vs. Control) and time (BL, 12-week) on MVPA (minutes/day). The null hypothesis is that there is no difference in change in MVPA in the Intervention group compared to the Control group. The alternative hypothesis is that there is a difference between groups. The nature of the hypothesis is confirmatory as this study has been powered to detect a difference should one exist. The mixed-effect model will be used to calculate the mean and 95% Confidence Interval time in MVPA at each study time point. We will also calculate the difference in means and 95% Confidence Intervals between the Intervention and Control group at each study time point. We will also calculate 2-sided p-values to determine statistical significance of differences between groups by time in MVPA. Data will be summarized by intervention group. Means, Standard Deviations, Minimums and Maximums will be used to summarize continuous variables. Categorical variables will be summarized as frequencies and percentages.

Mixed-effect modeling will be used to estimate MVPA over time. The mixed-effect model using restricted maximum likelihood estimation is a full information approach and leads to unbiased model parameter estimates in the presence of MCAR or MAR missingness. Selection between models with two common covariance structures, Toeplitz and independent errors, will be accomplished using the Akaike Information Criterion (AIC).

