### 9.5 Primary Efficacy Analysis

The primary endpoint of our study is to examine the efficacy of a physical therapist-delivered exercise intervention (Delaware PEAK, referred to as the Intervention) to increase MVPA over 12 weeks compared to a control group receiving web-based resources about knee OA and exercise (referred to as the Control).

The statistical model underlying this analysis is a mixed-effects model to examine the main and interaction effects of *group* (Intervention vs. Control) and *time* (baseline, 12-week) on MVPA (minutes/day).

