### Supplemental table 3: Per protocol sample change within and between groups

 <sup>13 MVPA: Moderate to Vigorous Intensity Physical Activity
  Treatment Beliefs of OA: Physical Exercise

<sup>15 Treatment Beliefs of OA: Physical Therapy SAP version 1.2: Delaware PEAK3/1/24

Supplemental table 4A: Secondary Data Analysis Sample (Per protocol sample excluding those who wore the ActiGraph monitors outside of the established visit windows) sample adjusted mean (se)

Outcome [adjusted	Baseline	12 weeks	24 weeks	P value
mean (se)];n				
Primary Outcome				
MVPA  (min/day)				
Secondary Outcomes				
Light Intensity				
Physical Activity				
Steps/day				

Supplemental table 4B: Secondary Data Analysis Sample (Per protocol sample excluding those who wore the ActiGraph monitors outside of the established visit windows) scores for study outcomes across time change within and between groups

Outcome	Adjusted Mean (se) change within groups				Adjusted Mean (se) change between groups	
	12 weeks – Baseline		24 weeks – Baseline		12 weeks – Baseline	24 weeks – Baseline
	Intervention Group	Control Group	Intervention Group	Control Group	(Intervention – Control)	(Intervention – Control)
Primary Outcome						
MVPA (min/day)						
Secondary Outcomes						
Light Intensity Physical Activity						
Steps/day						

<sup>16 MVPA: Moderate to Vigorous Intensity Physical ActivitySAP version 1.2: Delaware PEAK3/1/24Page 32 of 38

Supplemental table 5: Safety Analyses

Participants n/N (%)	Intervention Group	Control Group
Discontinued participation because of adverse events		
Serious Adverse Event (related or unrelated)		
Hospitalizations (related)		
Hospitalizations (unrelated)		
Deaths (related)		
Deaths (unrelated)		
Nonserious Adverse Event (related or unrelated)		
Back (related)		
Back (unrelated)		
Hip/Thigh (related)		
Hip/Thigh (unrelated)		
Knee (related)		
Knee (unrelated)		
Ankle/Foot (related)		
Ankle/Foot (unrelated)		
Other (related)		
Other (unrelated)		

Supplemental table 6: Comparison of included study participants with valid MVPA data (n=) vs those excluded from this analysis (n=)

Characteristic [mean (sd) or n (%)]	Study Participants	Study participants
	with valid MVPA data (n=)	excluded from MVPA analysis (n=)
	· · · ·	
Age (years mean (sd))		
Weight (kg mean (sd))		
Height (m mean (sd))		
Body Mass Index (kg/m  mean (sd))		
Gender (n (%))		
Women		
Men		

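### SAP 8.4 tests whether age, sex and BMI predict missing data but gives a positive result no analytic consequence, and the primary MVPA model omits all three

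*SAP*

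**What the plan says.** SAP 8.4 examines missing data in two steps. First, "missing data will first be summarized by group, time, each design cell, and each of the three covariates, age, sex and body mass index". Then, formally, "missing/non-missing will be taken as a dichotomous outcome in a logistic regression for continuous covariates", with chi-square tests for sex and for the design factors. Significant results "indicate a pattern of missingness variation that will be identified and reported and whose impact on the analysis will be explained if possible". No adjusted model, imputation or sensitivity analysis is attached to that outcome.

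The primary model in SAP 9.4 examines the "main and interaction effects of group (Intervention vs. Control) and time (BL, 12-week) on MVPA (minutes/day"); 9.5 repeats these terms. The only stated route for a covariate into a model is SAP 8.3, which selects covariates from baseline differences between the groups.

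On bias, SAP 9.4 says that the REML mixed model "leads to unbiased model parameter estimates in the presence of MCAR or MAR missingness". Section 8.4 makes a similar conditional statement and adds that if missing values are more frequent than assumed "or are truly missing not at random (MNAR), the analysis may be biased".

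Protocol 8.3, 8.4, 10 and 10.1 are the same on these points.

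**The concern.** A likelihood-based mixed model may ignore the missing-data mechanism when missingness depends only on quantities that the fitted model contains. Here these are group, time and the observed MVPA values, with baseline MVPA as one of the outcomes. Suppose that loss of 12-week data depends on BMI, and that BMI predicts 12-week MVPA even after baseline MVPA is known. The data are then MAR given BMI, but not MAR given what the model holds. This is a pattern that 8.4 goes looking for. BMI can be balanced between arms at baseline and still predict dropout, so 8.3 would not bring it in.

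At stake is the MVPA comparison that SAP 9.4 calls confirmatory. This is a separate matter from MNAR: the variables that would remove the bias come from the baseline form (SAP 6.4), and SAP 7 requires baseline assessments to be complete before randomization. A difference in pattern between arms is plausible, because participants are unblinded (SAP 6.3) and one arm has physical therapist consultations while the other has web resources. The documents give no evidence that it occurs.

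**Working it through.** **The plan's own figure.** SAP 7 gives 100 randomized and no effect size, SD, power or dropout rate, so the number cannot be reproduced. For scale only: with 50 per arm (1:1 assumed), two-sided 0.05 and 80% power, the detectable difference is √(2 × (1.96 + 0.84)² / 50) ≈ 0.56 SD.

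**Inputs from the documents.** Model terms: group, time, group-by-time (SAP 9.4, 9.5). Variables tested for missingness: group, time, age, sex, BMI (8.4). Trigger for covariates: baseline differences (8.3).

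**Assumed inputs, none in the documents.** 50 per arm; MVPA SD 20 min/day; baseline to 12-week correlation 0.6; no true effect; 25% missing in control, with odds ratio (OR) 1.5 to 3 per SD of BMI; 15% missing in the intervention arm, unrelated to BMI; correlation r of BMI with 12-week MVPA given baseline, 0.2 to 0.4 in size.

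**Step 1: formula.** Take BMI in SD units (X), unrelated to baseline MVPA. The effect of X on 12-week MVPA given baseline is β = r × 20 × √(1 − 0.6²) = 16r min/day. Without X in the model, the bias in an arm's 12-week mean is β × E(X | observed). The bias in the contrast is the difference of the two arm biases, so equal selection with equal β cancels.

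**Step 2: shift in X among those observed.** With logit P(missing | X) = a + log(OR) × X and a set for 25% missing, numerical integration over a standard normal X gives |E(X | observed)| = 0.098 for OR 1.5, 0.159 for OR 2 and 0.228 for OR 3. In the intervention arm the shift is 0.

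**Step 3: size of the contrast bias, min/day.** The simulations fit the two-visit likelihood estimate, 6,000 runs per setting.

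| Setting | Formula | Simulated, X omitted | Simulated, X included |
|---|---|---|---|
| r 0.2, OR 1.5 | 3.2 × 0.098 = 0.31 | 0.33 | 0.00 |
| r 0.2, OR 2 | 3.2 × 0.159 = 0.51 | 0.62 | 0.08 |
| r 0.4, OR 2 | 6.4 × 0.159 = 1.02 | 1.08 | −0.03 |
| r 0.4, OR 3 | 6.4 × 0.228 = 1.46 | 1.71 | 0.03 |
| r 0.3, OR 2 in one arm and 0.5 in the other (formula: 25% missing in each) | 4.8 × (0.159 + 0.159) = 1.53 | 1.62 | −0.04 |

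Monte Carlo error is about 4.0/√6000 = 0.05. A repeat simulation of the fourth row gave 1.40, so the top of the range is better read as 1.4 to 1.7. The standard error was 3.9 to 4.2 in all settings and did not rise when X was added. Hence 0.33/4.0 ≈ 0.1 and 1.71/4.0 ≈ 0.4 standard errors. A shift of that size moves the two-sided type I error from 5% to between 5.1% and 7.1%.

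**Step 4: when the contrast is and is not affected (SD units).** Separate large-sample runs assumed X correlated −0.3 with baseline MVPA, log-odds of missingness ±0.7 per SD of X, and 20% missing unless stated. Monte Carlo error is about 0.004.

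- X predicts missingness but not 12-week MVPA given baseline: contrast bias at most 0.006, which is none.
- X predicts both, equally in both arms: each arm's change is biased by about 0.02 to 0.03, the contrast by at most 0.006.
- X drives missingness in one arm only: 0.018 to 0.036 (X effect −0.15 to −0.3); 0.052 at 30% missing with effect −0.3.
- Opposite directions by arm: 0.041 to 0.068. At 30% missing the arm biases are −0.050 and 0.054, so the contrast is 0.104, about 19% of 0.56 SD.
- X effect differing by 0.2 SD between arms, equal missingness slopes: 0.026 to 0.034 in size.

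**Step 5: which model terms remove it.** A small, noisy REML check with one-arm selection gave group-by-time bias of 0.044 SD with no X, 0.028 with a main effect only, and −0.002 with X-by-time and X-by-group-by-time. Where the X effect itself differs by arm, bias was 0.031 SD without X, 0.030 with X common to both arms, and about 0.002 with X-by-group. Covariate-by-time terms alone therefore do not cover that last case.

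**The case against.** The strongest reply is that a positive 8.4 test proves little. It shows that a covariate predicts missingness. Bias in the contrast also needs that covariate to predict 12-week MVPA beyond baseline MVPA, and needs the missingness pattern or the covariate effect to differ by arm. This stands, and step 4 confirms it. A reader might infer that a significant test means a biased primary result; the documents and the arithmetic do not support that.

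A reader might also infer that the SAP's unbiasedness sentence is false. It is not: both 8.4 and 9.4 make it conditional on MCAR or MAR, and 8.4 concedes possible bias otherwise. What is missing is any statement of which variables MAR is conditional on, and any response when the check points outside them.

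Three further inferences go beyond the text. First, that the 8.4 regressions pool the arms: 8.4 summarizes missingness by group and design cell and does not say whether the regressions carry a group term. Second, that the table headed "Comparison of included study participants with valid MVPA data" (Supplemental table 6) hides differential 12-week dropout. It has no split by arm, but under 9.4 anyone with valid baseline wear stays in the analysis, so it may describe baseline exclusions only. Third, that covariates are ruled out: 8.4 calls age, sex and BMI covariates, and Supplemental tables 4A and 4B report adjusted means. That leaves the matter open, but no section puts these variables into the primary model.

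Finally, the sizes rest wholly on assumed inputs, with settings chosen to produce bias. This also stands. It limits the weight of the point, but not the case for a nearly free correction.

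**Conclusion.** The point holds in a limited form. As written, the protection claimed under MAR does not extend to missingness that depends on age, sex or BMI, which are the three covariates that 8.4 checks, and a positive check leads only to a report. Arm-specific changes can then be biased. The treatment contrast can be biased only if the covariate also predicts 12-week MVPA given baseline and the arms differ in missingness pattern or covariate effect.

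The likely size is modest: about 0.3 to 1.7 min/day, or 0.1 to 0.4 standard errors, at 50 per arm, SD 20 min/day, correlation 0.6 and 15 to 25% missing. With 30% missing and opposite selection by arm it reaches about 0.10 SD. None of these inputs is in the documents. The change is worth making before the analysis because it costs almost nothing and avoids an unplanned choice of model after a positive test; the point does not by itself put the primary result in doubt.

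**What to change.** - In SAP 9.4 and 9.5, state that the primary MVPA model includes age, gender and BMI, centred, each with its interaction with time, regardless of the 8.4 tests. A main effect alone is not enough. Section 8.4 says sex while the baseline form records gender, so name the variable used.
- Add a sensitivity analysis in which the covariate effects may differ by arm: covariate-by-group-by-time terms, or multiple imputation by arm using these variables.
- Reword the unbiasedness sentences in 8.4 and 9.4 so that they refer to missingness depending on variables in the model.
- Run the 8.4 regressions with a covariate-by-group term, since a difference between arms is what threatens the contrast.

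The cost is SAP wording and a few degrees of freedom out of about 100 participants. The form in SAP 6.4 already collects date of birth, gender, height and weight at baseline. The simulations with X added showed no loss of precision, but they added one covariate. The group-interaction terms will cost more, which is why they belong in the sensitivity analysis.

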#### 8.2.3 Secondary Data Analysis Sample

• We will repeat the Per Protocol analysis for outcomes measured with the ActiGraph excluding participants on those who worn their ActiGraph monitor outside of our established visit windows.

The exact process for assigning the statuses (Full Analysis Sample and Per Protocol

Sample) will be defined and documented prior to breaking the blind along with any predefined reasons for eliminating a subject from a particular population.

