#### Table 2: Mean (sd) scores for study outcomes across time by treatment groups

 <sup>2 MVPA: Moderate to Vigorous Intensity Physical Activity
  Treatment Beliefs of OA: Physical Exercise

<sup>4 Treatment Beliefs of OA: Physical Therapy SAP version 1.2: Delaware PEAK3/1/24

Outcome [mean (sd) or n (%)]	Mean (sd) cha	-			Change betw Intervention Baseline –	
	Baseline – 12 weeks		Baseline – 24	Baseline – 24 weeks		Baseline – 24 weeks
	Intervention Group	Control	Intervention Group	Control	Mean difference (95% CI)	Mean difference (95% CI)
Primary Outcome						
MVPA  (min/day)						
Secondary Outcomes						
Light Intensity Physical Activity						
Steps/day						
Treatment Beliefs						
TOA-PE 						
positive						
TOA-PE						
negative						
$TOA-PT^7$						
positive						
TOA-PT						
negative						
Exploratory						
Outcomes						
VAS pain						
KOOS pain 						
KOOS ADL 						
Exercise						
Adherence						

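### Is the confirmatory MVPA test left undefined because SAP 8.4 does not say whether a Box-Cox model would replace the minutes/day model?

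*SAP*

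**What the plan says.** SAP 8.4 sits under the missing-data heading but also covers model checking. Residuals are to be examined with Shapiro-Wilk and a test of equal variances, and "transformations, if necessary, will be chosen from among the Box-Cox transformations". Protocol 8.4 has the same sentence.

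SAP 9.4 describes the main model, with MVPA in minutes/day, and gives its status: "The nature of the hypothesis is confirmatory as this study has been powered to detect a difference should one exist". On reporting it says: "We will also calculate the difference in means and 95% Confidence Intervals between the Intervention and Control group at each study time point". SAP 9.5 repeats the time factor and outcome as "baseline, 12-week) on MVPA (minutes/day", again without mentioning transformation.

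The shells in SAP 15 follow suit. The between-group columns of Table 3 are headed "Mean difference (95% CI", closing bracket omitted, with the MVPA row in min/day. Supplemental tables 4A and 4B ask for a "sample adjusted mean (se", bracket again omitted, and for the "Adjusted Mean (se) change between groups".

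SAP 6.3 says the statistical analyses will be done blinded. SAP 8.2.3 requires that the process for assigning analysis populations "will be defined and documented prior to breaking the blind". It sets no such requirement for the scale of analysis.

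**The concern.** Device-measured MVPA is bounded at zero and could well be right-skewed, so the residual checks may fail. SAP 8.4 then points to a transformed model, while 9.4, 9.5 and the shells still describe a difference in means in minutes/day. A group-by-time contrast on a log or power scale is a different quantity from a difference in change in minutes/day. If one analyst replaced the model and another ran the transformed version alongside it, they could reach different verdicts on the one hypothesis labelled confirmatory. The plan also gives no threshold for the checks, no rule for lambda, no handling of zeros (ordinary Box-Cox needs positive values, and SAP 6.4 gives a range starting at 0), and no route back to the minutes/day cells.

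**Working it through.** **1. The plan's own figures.** There is none on this point to reproduce. SAP 7 gives 100 randomised participants, with no effect size, SD, power or dropout. An even split of 50 per arm is assumed, since blocks of 4 are stated but not the ratio. Two-sided 0.05 is assumed from the 95% intervals.

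**2. Reading the clause.** The sentence in 8.4 runs in order: check the residuals, then transform if necessary. That describes a repair to the model just checked. Where the SAP wants a second analysis beside the main one, it says so: out-of-window data (6.4 and 8.2.3), the per-protocol analysis of the primary endpoint (9.6.1), and separate ITT and per-protocol analyses (9.6.2 and 9.7). It never calls a transformed model a sensitivity analysis. Replacement is therefore the natural reading, though it is not stated.

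**3. Does either choice damage the test?** Illustrative simulation, all inputs assumed: log-normal MVPA, median 12 min/day, within-person correlation 0.7, 50 per arm, complete data, 3,000 runs per row. With two times and complete data, the group-by-time test equals a two-sample t-test on change. The Box-Cox version uses MVPA + 1 with lambda chosen by likelihood. Under the rule, the transformed p-value is used if Shapiro-Wilk p<0.05. Monte Carlo SE is at most √(0.5 × 0.5 / 3000) = 0.9 points, and √(0.05 × 0.95 / 3000) = 0.4 points near 5%.

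| log-SD | Effect | Raw, % significant | Box-Cox, % | Rule, % | Verdicts differ, % |
|---|---|---|---|---|---|
| 0.3 | none | 5.1 | 5.1 | 5.1 | 2.4 |
| 0.6 | none | 5.1 | 5.3 | 5.3 | 4.8 |
| 0.9 | none | 3.9 | 4.7 | 4.7 | 5.5 |
| 0.3 | ×1.4 | 100 | 100 | 100 | 0.0 |
| 0.6 | ×1.4 | 89.3 | 93.5 | 93.5 | 7.4 |
| 0.9 | ×1.4 | 47.4 | 65.4 | 65.4 | 26.9 |
| 0.3 | +5 min/day | 100 | 100 | 100 | 0.0 |
| 0.6 | +5 min/day | 88.0 | 98.9 | 98.9 | 10.9 |
| 0.9 | +5 min/day | 33.3 | 88.0 | 88.0 | 54.9 |

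Shapiro-Wilk fired in 97.6% to 100% of runs. Reporting whichever test was significant, which 8.4 does not license, gave false-positive rates of 6.3%, 7.6% and 7.0% at log-SD 0.3, 0.6 and 0.9.

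**4. Other shapes.** A second set of runs assumed a mean of 15 min/day, 15% missing at 12 weeks and a two-time REML model. With no effect, rejection under the trigger was 4.6% to 6.1%. At +5 min/day the verdicts differed in 0.0% of trials for near-symmetric MVPA, 0.5% to 3.7% for gamma shape 4, 7.6% to 12.8% for gamma shape 2, and 23.9% to 48.5% for log-normal with log-SD 0.9. Neither scale always wins: for gamma shape 2 with a proportional effect, power was 68% raw, 66% square root and 55% log. The decimals are soft. In that last setting 8.6% of trials lost significance on transforming and 4.2% gained it; a repeat with 1,000 runs gave 5.3% and 2.6%. None of these runs contained zeros.

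**5. The table cell.** A log-scale ratio of 4/3 corresponds to (4/3 − 1) × reference level: 10/3 = +3.3, 15/3 = +5.0 or 25/3 = +8.3 min/day at reference levels of 10, 15 and 25. A transformed contrast therefore does not fill the min/day cell unless a reference level or another convention is stated.

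**The case for a change.** The strongest case for a change is that a confirmatory test should be fixed in advance, and here it is not fully fixed. Replacement is an inference. It sits awkwardly with 9.4, 9.5 and the Table 3 shell, which keep to minutes/day, and an analyst who accepts it still has no instruction for the modelled cells. Blinding limits choosing a scale by its result but does not say which result is primary, and masked group codes still show whether two arms differ. One sentence would settle it.

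The omission stands: trigger, lambda, zeros and effect measure are unspecified, and nothing else in either document supplies them. The claim of two equally compliant confirmatory tests does not stand, given how 8.4 reads and how the SAP marks its parallel analyses elsewhere. The disagreement rates compare replacement with a sensitivity-only reading that the text hardly supports, so they do not measure the gap that remains. Supplemental tables 4A and 4B concern a per-protocol subset excluding out-of-window wear and do not carry the confirmatory test. The clause does not name MVPA, but the mixed model is the only outcome model that 8.4 describes, so applying it there is reasonable.

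**Conclusion.** No change to the plan is needed. This is missing working detail, together with a fair trade-off. Neither scale is wrong, and type I error is not at issue: false-positive rates were 3.9% to 5.3% for each test alone, and 4.6% to 6.1% across both sets of runs when the trigger was applied. The scale affects power and interpretation. Strong skew often favours a transformed model, while minutes/day gives a directly readable effect.

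An analyst following 8.4 can choose lambda by likelihood, add a small constant if zeros occur, and name the scale when reporting the p-value. The commitment in 9.4 to a difference in means still leads to a minutes/day contrast in Table 3, labelled by the model it came from. This is ordinary practice.

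The effect on this trial's verdict cannot be determined from the documents. It is nil if MVPA is near-symmetric and the effect is about 5 min/day, and could reach about half of trials under the most skewed shapes assumed. These figures rest on 50 per arm, a correlation of 0.7 and assumed MVPA distributions, none of which the plan states.
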